#### **Qualitative Interviews**

Semi-structured qualitative interviews will be conducted by RA and/or LR over the telephone with a sample of those who at the end of the intervention period agree to participate in a 1:1 interview. We will conduct interviews at two timepoints; 3m and 6m for the intervention group and 6m only for the wait-list control group. Sampling will aim to include 20 participants from the intervention group (10 different patients selected at each time point 3 months and 6 monthsthis will allow us to see if people continue to use the intervention beyond the 3 month period patients will only be interviewed once) and 10 people from the wait-list control group (after completing 6m in the study) = Total of 30 interviews. Audio-recorded interviews will be transcribed by an approved supplier who has signed a confidentiality agreement. We will seek to determine drivers for and barriers to the use of this self-help intervention by interviewing those who are allocated to receive the intervention treatment who do not start or drop out prior to the end of the intervention period and facilitators to the treatment among those who use the lymphatic self-massage technique to all or some extent, and to the feasibility study in general also sampling those in the control arm. A thematic approach will be adopted for the analysis and Public and Patient Involvement (PPI) team will be involved in discussions around the emergent themes and to ensure correct meanings are attributed to participant comments. Findings will also then be used to inform potential future larger studies using this intervention.

Audio recordings will be destroyed after transcription.

#### 7.2 Inclusion / Exclusion Criteria

This will be achieved by eligibility screening conducted using FARSITE prior to Phase 1 invitation by patients GPs. At Phase 2 consent process, participants eligible from Phase 1 will be asked to confirm that they meet eligibility criteria and none of the exclusion criteria.

#### Inclusion Criteria:

Participants aged 18 or over

COVID positive result recorded since July 2020

For the Phase 2 intervention a CFQ score >4 when scored binomially.

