#### Phase 1: Survey to determine prevalence of 'Long COVID' in primary care

Patients will be recruited from general practice and provided a link to complete an online survey to determine levels of fatigue (physical and mental) using the Chalder fatigue Questionnaire – CFQ), physical functioning using SF-12 and quality of life using EQ5D at least 12 weeks after previously testing positive (SARS CoV-2) for COVID-19.

The results of CFQ will be used to screen respondents for 'Long COVID' with those scoring >= 4 on CFQ scored bimodally, being invited to participate in Phase 2 RCT. This will be advised on screen explaining that the symptoms they reported mean they are suitable to join the second phase of the study. A tick box on screen will allow those interested in participating to view a copy of the Participation Information Sheet (PIS) and Consent Form (CF) on screen and also receive a copy by email or post. Interested participants will be asked to provide their telephone number so the research practitioner can call them back to answer any questions they might have about the study and to take informed consent over the telephone for those who agree to participate. The data collected in the Phase 1 Survey will be used as the proxy baseline data for Phase 2 to reduce the need for participant to repeat measures unnecessarily.

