#### Phase 1: Post COVID Survey

Patients meeting study inclusion criteria will be invited to take part in a survey of the long-term effects of COVID-19. Participants will be sent an invitation letter by their GP and a participant information sheet. The letter will include an online link and when patients log onto the website, they will be asked to confirm their participation in the survey which will be by implied consent, used in lieu of patients having to sign and return paper consent forms. Participants will be allocated a survey participant ID number and once the box is ticked indicating they give consent, they will be prompted to complete measures on the following:

- fatigue using the Chalder Fatigue Questionnaire (CFQ) (Chalder et al. 1993),
- physical functioning using the Short Form SF-12 (Gandek,et al.1998) and
- quality of life EQ5D5L (Rabin & Charro. 2001)

plus demographic information (age, sex, start date of COVID-19 symptoms, date of positive COVID-19 test, tick box of symptoms, whether they were hospitalised with COVID-19 and if so dates and whether they received breathing support and what type (Oxygen, CPAP, Ventilation).

Patients scoring 4 or more on the CFQ (when scored binomially) will be invited to participate in Phase 2. A screen pop-up will inform those meeting screening criteria that their reported symptoms make them eligible to take part in the next phase of the study to try to help reduce fatigue associated with Long COVID.

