#### 7.5 Outcome measurement

- 1. To determine the participation rate for an online survey of Long COVID within general practice.
- 2. To determine the prevalence of Long COVID using a case cut-off of 4 or above on the CFQ (binomially scored)
- 3. To determine recruitment and retention of participants into an RCT which tests a lymphatic self-massage intervention over 6 months to alleviate fatigue related symptoms for those affected by the longer-term sequelae of COVID-19.

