# 10 Statistical analyses and data handling

#### Analysis

This is a feasibility study, so we will not be carrying out formal hypothesis testing to determine if the intervention is effective. Data analysis will follow an Intention-To-Treat (ITT) protocol and will be used to inform power calculations for a definitive trial in addition to other published sources. Attrition and reasons for drop-out will be recorded where possible. We will assess rates of missing data (and which elements in particular) and proportions of dropouts at different trial stages. We will also assess whether any of the measures display floor and/ or ceiling effects.

We will calculate and present in a CONSORT (Eldridge et al, 2010) flow chart: the proportion of people with CFQ scores greater than or equal to 4, consenting to the study; those entering the randomised phase; the proportion completing 50% and 100% intervention (using patient reported compliance sheet); the proportion completing follow-up assessments at 3 and 6 months post-randomisation.

We will summarise, as appropriate (e.g. mean/ standard deviation; median/ inter-quartile range; proportion/ 95% confidence interval; data range) data for all potential outcome measures, overall and by group. Outcome data and changes (mean differences) in patient-reported measures between baseline (initial clinical assessment) and 3 and 6 month follow-up will be plotted with 95% confidence intervals by randomisation group on an intention to treat basis.

Adherence with the intervention will be measured and used to calculate an estimate of dose response. Where participants adhere to all 3 stages of the intervention fully – using the intervention as intended daily this will be deemed full intervention, with non-use of any stages of the intervention as a zero dose.

The SD of the (potential) Primary Outcome, along with the estimated attrition rate and the average number recruited per PCT/CCG (plus the range of this data) will be used to help inform the sample size calculation for the large-scale RCT.

The Primary feasibility outcomes will be recruitment and retention rates, and we will gain an estimate of likely effect sizes of the self-help intervention for a range of outcome measures and based on this determine the appropriate sample size for a larger trial to evaluate its effectiveness and cost-effectiveness versus standard treatments delivered within an NHS CFS/ME Service.

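### Section 7.2 sets Phase 2 inclusion at CFQ above 4, while the invitation rule, case cut-off and CONSORT proportion all use 4 or more, so a score of exactly 4 is invited but ineligible as written

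*Protocol*

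**What the plan says.** Five places in the protocol state a CFQ threshold.

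- Section 7.2, Inclusion Criteria: "For the Phase 2 intervention a CFQ score >4 when scored binomially".
- Section 6, Phase 1 survey: the CFQ result screens respondents, with "those scoring >= 4 on CFQ scored bimodally, being invited to participate in Phase 2 RCT".
- Section 7.1, Phase 1: Post COVID Survey: "Patients scoring 4 or more on the CFQ (when scored binomially) will be invited to participate in Phase 2". The same section adds: "A screen pop-up will inform those meeting screening criteria that their reported symptoms make them eligible to take part in the next phase".
- Section 7.5, Outcome measurement: prevalence is to be determined "using a case cut-off of 4 or above on the CFQ".
- Section 10, Analysis: the CONSORT flow chart will show "the proportion of people with CFQ scores greater than or equal to 4, consenting to the study".

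The opening of Section 7.2 says that, at Phase 2 consent, people found eligible in Phase 1 confirm that they satisfy the eligibility criteria. Section 10 names recruitment and retention rates as the primary feasibility outcomes. Section 8.3 requires any protocol deviation to be reported to the sponsor within 24 hours.

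**The concern.** A total made by scoring each item as present or absent is a whole number, so above 4 means 5 or more. The two rules therefore part company at one value, a score of exactly 4. A person with that score is invited, is told that they qualify, counts as a Long COVID case and enters the CONSORT count, but does not meet the inclusion list.

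The inclusion list is what research staff, monitors and auditors apply. It leaves staff two courses for a person scoring 4: randomise them against the written criterion, or turn away someone whom the survey has just told they are eligible. The first produces reportable deviations. The second affects a primary feasibility measure, because people who cannot be enrolled stay in the denominator of the consent proportion.

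**Working it through.** **Is there a reading under which the statements agree?** One possibility is a case definition of 4 or more for prevalence and a deliberately stricter rule for the trial. Sections 6 and 7.1 rule this out, because both tie 4 or more to the Phase 2 invitation itself. The conflict is confined to Phase 2 entry. The Section 7.2 threshold is written for Phase 2 only, so the prevalence estimate is untouched.

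**Inputs (Section 7.1, Recruitment procedure).** 4000 invitation letters; 2000 survey responses (50%); a Long COVID rate of 10%; 50% uptake into Phase 2.

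**The plan's own figure.** 4000 × 0.50 = 2000; 2000 × 0.10 = 200 screen-positive; 200 × 0.50 = 100 randomised. This reproduces the planned 100, with uptake 100/200 = 50%.

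**Assumption.** Let s be the share of screen-positives scoring exactly 4. The protocol gives no CFQ distribution, so s is assumed to lie between 5% and 20%. Uptake is taken as 50% at every score.

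**People invited but ineligible as written:** 200 × s.
- s = 5%: 10
- s = 10%: 20
- s = 20%: 40

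**If the screening rule is followed.** All 200 can consent, 100 are randomised and uptake is 100/200 = 50%. Of the 100, 100 × s fall outside Section 7.2:
- s = 5%: 5
- s = 10%: 10
- s = 20%: 20

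**If Section 7.2 is enforced.** Eligible = 200 × (1 − s); randomised = half of that. The CONSORT proportion still divides by 200:
- s = 5%: 190 eligible, 95 randomised, 95/200 = 47.5%
- s = 10%: 180 eligible, 90 randomised, 90/200 = 45%
- s = 20%: 160 eligible, 80 randomised, 80/200 = 40%

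Among those actually eligible, uptake is 50% in each row (95/190, 90/180, 80/160). The shortfall comes entirely from the mismatched denominator.

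**The case against.** Four of the five statements agree, including the rule that drives the automatic screen, so Section 7.2 is probably a slip. The screen decides CFQ eligibility before consent. The protocol nowhere says that participants are told their score, so they could hardly rule themselves out at exactly 4 when asked to confirm the criteria. This stands. It makes enrolment against the written criterion the likelier outcome, and a distorted uptake rate the less likely one.

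The protocol plans no formal hypothesis testing, and the 100 does not come from a power calculation. Screening precedes randomisation, so either rule applies equally to both arms. This also stands, and it limits the severity.

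The sign in Section 7.2 might have lost a bar when the text was read from PDF. That cannot be excluded, but Section 6 keeps its typed greater-than-or-equal sign and nothing in the text supports this explanation. The sponsor can check the source file at once.

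Three stronger readings are tempting:
- **The recruitment rate will be biased.** The documents support this only if Section 7.2 is enforced at consent. If the screening rule is followed, numerator and denominator agree.
- **The affected share can be worked out from the score range.** The protocol states neither the range nor the distribution, so no single figure can be derived.
- **Enforcement would raise uptake.** Holding consents at 100 while the eligible set shrinks to 190 or 160 gives 100/190 = 52.6% or 100/160 = 62.5%. That requires uptake among eligible people above the protocol's 50%, and it drops the CONSORT denominator that Section 10 specifies.

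**Conclusion.** The inconsistency is real and nothing elsewhere in the protocol resolves it. Under an assumed 5% to 20% share at exactly 4, it touches 10 to 40 of the 200 expected screen-positives. The likelier consequence is 5 to 20 of the 100 randomised standing as deviations from Section 7.2. If the stricter rule is enforced instead, 95 to 80 are randomised and uptake reads 47.5% to 40%. These sizes depend on the assumed share and on uptake not varying with score; the contradiction depends on neither. It should be fixed, but as an internal inconsistency: the documents do not support calling it a design flaw or a source of bias between the arms.

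**What to change.** In Section 7.2, change the Phase 2 threshold from CFQ above 4 to CFQ 4 or more, to match Sections 6, 7.1, 7.5 and 10. Confirm that the survey's automatic eligibility branch uses the same rule. With that change the planned funnel stays at 200 eligible and 100 randomised. The cost is a one-line protocol amendment and one check of the survey logic, best done before launch. If the stricter threshold was in fact intended for Phase 2, the invitation text in Sections 6 and 7.1 and the CONSORT proportion in Section 10 would have to change instead.

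The scoring method is called bimodal in Section 6 and binomial in Sections 7.1, 7.2 and 7.5. That is a separate point of terminology; it can be tidied in the same amendment but does not affect this one.

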#### **Exclusion Criteria:**

Currently living in a Care Home setting

Pregnant and lactating women.

End stage heart failure, cancer, major mental illness and primary sleep disorders (alternative causes of fatigue).

Dementia

#### 7.3 Study duration

Participants are enrolled in the study for a maximum of 6 months.

The project will run for Fifteen months (1 month lead in time, 4 months recruitment phase plus 6 months follow-up for intervention study and an optional qualitative interview for n=30 participants) plus 4 months analysis and write up time and submission of final reporting.

#### 7.4 Consent procedure

Because this is a two-stage study there are two separate consent points:

Phase 1: Survey

Patients with a previous positive SARS-CoV-2 test for COVID 19 who received a letter from their GP and opened a link to complete the survey will before starting to provide their survey responses be directed to our consent statement. Participants will be asked to tick the relevant consent clauses and by virtue of completing the survey participants are providing implied consent to take part in this survey.

Only participants who meet screening criteria for 'Long COVID' within the survey will be invited to participate in Phase 2.

Phase 2: Intervention RCT

Potential participants will be shown a message that they are eligible for the next phase of the study and potential participants will see the Phase 2 participant information sheet (PIS) and consent form (CF) after completing the survey. They will have the option to receive copies of these by email or by post.

Participants who wish to join the Phase 2 study will be asked to enter their name and contact telephone number and an email. A Research Practitioner will then telephone the potential participant and go through the consent form with them over the telephone. At this point they will be able to ask any questions they might have about participating ahead of providing informed consent.

A copy of the telephone consent will be retained by the Research Practitioner at Salford Care Organisation and a copy sent to participants along with details of their randomisation.

#### 7.5 Outcome measurement

- 1. To determine the participation rate for an online survey of Long COVID within general practice.
- 2. To determine the prevalence of Long COVID using a case cut-off of 4 or above on the CFQ (binomially scored)
- 3. To determine recruitment and retention of participants into an RCT which tests a lymphatic self-massage intervention over 6 months to alleviate fatigue related symptoms for those affected by the longer-term sequelae of COVID-19.

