## 1 Study summary

#### Background

We know from previous worldwide pandemics of Severe Acute Respiratory Syndrome (SARS) and Middle Eastern Respiratory Syndrome (MERS), caused by viruses similar to that causing COVID-19, that whilst many people had a severe acute respiratory infection, many of those surviving, went on to develop long-term effects (Moldofsky & Patcai, 2011). Follow-up studies showed post-viral fatigue was still present up to five years later, impacting on peoples long-term functioning.

As hospitals learn how best to improve outcomes there are an increasing number of COVID-19 survivors. Many are now reporting persistent ongoing fatigue related symptoms (Huang et al., 2020). Both laboratory (Lu et al., 2020) and observational studies (Sun et al., 2020) suggest that this fatigue is a result of cytokine storm activity, centred largely in the brain and spinal cord (Paterson et al., 2020).

The fatigue related symptoms observed are similar to those seen in Chronic Fatigue Syndrome/Myalgic Encephalomyelitis (CFS/ME), a condition characterised by unremitting depletion of energy, lack of refreshing sleep, brain fog and profound fatigue after any significant mental or physical exertion (Perrin et al., 2020; Shepherd, 2019; MEA Association, 2020).

We propose trialling an adaptation of a brain and spinal lymphatic drainage technique for use by patients at-home. Self-massage of the head, neck and chest and alternating warm and cool gel packs on the upper spine encourages lymph drainage of the brain and spine along with gentle mobility exercises that improve spinal mobility. This technique is already widely used by patients with CFS/ME as a maintenance programme in-between receiving lymphatic drainage treatment in clinical settings. Whilst this intervention does not attempt to replicate what is delivered by physiotherapist and osteopathic practitioners, it offers a relatively low-cost self-help programme which can be delivered without the need for face to face intervention, important in the COVID-19 and post-COVID-19 landscape and for patients with persistent fatigue.

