# 5 Aims of the proposed research

- To estimate the prevalence of physical and mental fatigue, its' effect on physical functioning and quality of life in people who tested positive to COVID-19 previously in a primary care sample.
- To determine whether patients reporting fatigue associated with post COVID-19 post viral syndrome (long COVID) will participate in a 2-arm randomised control trial offering a lymphatic self-massage technique or a wait-list control group who will receive the intervention after 3 months.
- To determine the recruitment and retention rate of participants in such a trial and to assess follow-up rates at 3 and 6 months in both groups
- To understand the acceptability of the lymphatic self-massage technique to participants (via qualitative semi-structured interview) and to assess compliance with the regime suggested (via tick sheet to measure intervention adherence at follow-up).
- To determine possible effects of using the intervention vs not by comparing data from the intervention group and wait-list control group at 3 months.
- To determine possible effects of delaying the use of the intervention by comparing data from the intervention group and wait-list control group.

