#### 7.1 Recruitment procedure

We will invite Salford GPs to screen their adult patients (aged 18 or over) whose notes indicate a previous positive SARS CoV-2 test for COVID-19 and reported in the last 12 weeks or more to participate in a prevalence study of fatigue-related symptoms. Screening will be facilitated using the FARSITE system (Hosted by Northern Care Alliance NHS Foundation Trust & NW e-Health). FARSITE when used as anonymised intelligence tool indicated 14,083 patients with a previous positive COVID-19 test. We plan to invite up to 32 GP practices whose number of patients is greater than 100 per practice to participate in order to generate the n=2,000 survey responses expected to recruit the 100 patients required into our Phase 2 study.

GPs will send a letter inviting patients who meet the study inclusion criteria to participate in a survey to look at Long COVID symptoms and their impact with some people being asked to participate in an intervention study to try to help reduce fatigue levels. This will be funded by [name] PI fund at the Northern Care Alliance NHS Foundation Trust.

Survey respondents in Phase 1 will be allocated a survey Participant ID number. Survey completion will predominantly be online, although paper copies will also be available for patients without internet / computer access. To facilitate this, a Research Practitioner (RA) based in the Research Delivery Team at Northern Care Alliance NHS Foundation Trust will assign a number manually on the recruitment log and enter it on the paper survey form that will be sent by post for completion along with a reply-paid envelope. Pseudonymised participant ID number will allow the RA will enter and link data to its respective participant but without compromising the confidentiality of clinical responses received. ID numbers will allow linkage to GP practice to monitor recruitment rates and to permit accrual data to be collected for the Local Care Research Network (LCRN).

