Prior to FARSITE data being available, we had used recruitment trajectories based on a 'Recruitment Estimate' of 28,720 potentially eligible participants in Greater Manchester, equating to 2.9% with positive SARS-CoV-2 test recorded in their GP notes (FARSITE Data provided by Greater Manchester Comprehensive Research Network using data at April 2021). Applying this same rate to Salford's 226,000 adult population we anticipate identification of approximately 6,554 COVID-19 positive patients, although June data now suggest 14,083 eligible adults within Salford GP practices alone.

We anticipate that around 50% of those eligible to take part in the Phase 1 study will be willing to take part in the study, this number is based on 51% households in England participating in ONS Coronavirus Infection Survey (https://www.ons.gov.uk/peoplepopulationandcommunity/healthandsocialcare/conditionsanddi seases/bulletins/coronaviruscovid19infectionsurveypilot/previousReleases) although we expect uptake to an invitation via the patients GP may be higher.

\*Sponsor's representative: [name], Managing Director of Research & Innovation Norther Care Alliance NHS Foundation Trust, [name] [contact]; email: [contact]

Whilst work on infection rates has been the focus, there is much less work around the prevalence of Long COVID and individual symptoms, so we do not have confirmed percentages of those likely to meet CFQ cut-off scores. Data modelling by Northern Care Alliance NHS Foundation Trust surveillance unit however adopts a 'Long COVID' rate of 10% having symptoms at 4 weeks or longer, with fatigue being the major symptom (https://www.ons.gov.uk/peoplepopulationandcommunity/healthandsocialcare/healthandlifeex pectancies/datasets/prevalenceoflongcovidsymptomsandcovid19complications).

Assuming an uptake rate of 50% into the Phase 2 Intervention for those who meet the screening criteria based on CFQ agreeing to participate in the Phase 2 intervention, we should be able to recruit our proposed sample size of 100 by 4 months. This is based on invitation letters being sent out to 4000 patients, 2000 of whom we hope will participate in the survey, 200 of which may have Long COVID fatigue related symptoms, with 100 agreeing to participate in the intervention study.

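### Section 7.5 reports a CFQ score of 4 or more as Long COVID, but fatigue or CFS/ME that preceded COVID-19 is neither excluded nor asked about, so it will be counted as Long COVID

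*Protocol*

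**What the plan says.** The protocol names one survey figure in two ways.

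- **As fatigue.** The first aim in Section 5 is "To estimate the prevalence of physical and mental fatigue, its' effect on physical functioning and quality of life in people who tested positive" for COVID-19, in a primary care sample.
- **As Long COVID.** Section 7.5 has "To determine the prevalence of Long COVID using a case cut-off of 4 or above on the CFQ". Section 6 (Phase 1) applies the same rule: "The results of CFQ will be used to screen respondents for 'Long COVID' with those scoring >= 4 on CFQ scored bimodally". The first study question in Section 1 links the fatigue to Long COVID, and Section 4 gives the target as the prevalence of the post-COVID syndrome.

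On other causes of fatigue, Section 7.2 excludes "End stage heart failure, cancer, major mental illness and primary sleep disorders (alternative causes of fatigue"). Neither fatigue before COVID-19 nor CFS/ME is on the list. Section 1 describes the symptoms seen after COVID-19 as similar to those of CFS/ME, and says of the intervention: "This technique is already widely used by patients with CFS/ME as a maintenance programme".

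Besides the CFQ, SF-12 and EQ-5D-5L, the survey items in Section 7.1 are age, sex, start date of COVID-19 symptoms, test date, a symptom tick box, and details of hospital stay and breathing support.

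On response, the GP letter in Section 7.1 describes a "survey to look at Long COVID symptoms and their impact with some people being asked to participate in an intervention study" on fatigue. The same section states "We anticipate that around 50% of those eligible to take part in the Phase 1 study" will agree to take part.

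**The concern.** A fatigue score taken once, at least 12 weeks after a positive test, shows who is fatigued then. It does not show when the fatigue began or why. By listing exclusions as alternative causes of fatigue, the protocol accepts that attribution matters, yet it leaves out the condition that it describes as similar.

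The gap is in data collection. The survey records when COVID-19 symptoms started, but no listed item records when the fatigue started or whether CFS/ME was diagnosed earlier. An analysis plan cannot recover what was never asked.

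At stake is what the prevalence figure can be said to measure. There is also a smaller matter for the trial. A person with earlier CFS/ME who scores high enough could enter Phase 2, possibly already using the technique, and nothing in the protocol would record it.

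**Working it through.** **The plan's own figures (Section 7.1).** 4,000 invited × 0.50 = 2,000 responders. 2,000 × 0.10 = 200 with fatigue-related Long COVID. 200 × 0.50 = 100 randomised. All three reproduce. The 10% is the protocol's planning rate, which it gives for symptoms at 4 weeks or longer. It is used below only as a reference value.

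**Sampling error.** With 200 of 2,000, the 95% half-width is 1.96 × √(0.10 × 0.90 / 2,000) = 0.013, or 1.3 points (about 8.7% to 11.3%).

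**Fatigue from other causes.** Let p be the true proportion with Long COVID fatigue, and b the proportion of everyone else who score 4 or more for other reasons. With no selection, the survey shows p + (1 − p) × b. The protocol gives no value for b, so the values below are assumptions. Section 7.2 already removes some of this background.

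| b (assumed) | Survey shows, true p = 10% | Share that is Long COVID |
|---|---|---|
| 0% | 10% | 100% |
| 5% | 0.10 + 0.90 × 0.05 = 14.5% | 0.10 / 0.145 = 69% |
| 10% | 0.10 + 0.90 × 0.10 = 19% | 0.10 / 0.19 = 53% |

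The excess is 4.5 or 9 points, against a half-width of 1.3 points.

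**Self-selection, taken alone.** A true 10% of 4,000 is 400 cases. Hold overall response at 50%, so that 2,000 reply, and vary the response of cases (assumed).

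| Cases responding | Cases among responders | Response of non-cases | Survey shows |
|---|---|---|---|
| 40% | 160 | 1,840 / 3,600 = 51.1% | 160 / 2,000 = 8% |
| 50% | 200 | 1,800 / 3,600 = 50% | 200 / 2,000 = 10% |
| 60% | 240 | 1,760 / 3,600 = 48.9% | 240 / 2,000 = 12% |
| 70% | 280 | 1,720 / 3,600 = 47.8% | 280 / 2,000 = 14% |

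Fatigue from other causes can only raise a figure called Long COVID. Selection can move it either way.

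**The case against.** Several points on the other side are sound.

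- **The first aim is not wrong as worded.** A reader might infer that the first aim will itself return too high a figure because of prior fatigue. Section 5 asks for fatigue prevalence in people who tested positive, and prior fatigue belongs in that number. The fault lies in the Long COVID label elsewhere.
- **Prevalence is not the primary outcome.** Section 10 makes recruitment and retention primary, and the first study question asks whether an online questionnaire can be used to determine prevalence. This limits the weight of the point but does not remove it, because Section 7.5 still lists the prevalence of Long COVID as an outcome.
- **Selection need not be upward.** A reader might infer that a letter naming Long COVID and a treatment study must inflate the result. That is plausible, but the documents give no response rate by symptom status, and the most fatigued may be the least likely to reply. The participation rate is itself an outcome in 7.5, so non-response will be visible. Weighting is usually left to the analysis plan, and weighting on age, sex and practice would not remove response driven by symptoms.
- **The exclusions before invitation are not an error.** A reader might object that they restrict the denominator. They are a disclosed eligibility rule and would, if anything, lower the fatigue figure.
- **Contamination of the control arm is not shown.** Section 1 speaks of CFS/ME patients in general, nothing shows that any invitee uses the technique, and randomisation spreads prior users across the arms on average. Section 6 also leaves usual care unconstrained on purpose. What remains is that prior use would go unrecorded.

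None of this answers the central fact: the outcome is named Long COVID, and the listed data cannot tell new fatigue from old.

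**Conclusion.** The point holds as a cheap improvement to the definition and the data collected. As written, Sections 6 and 7.5 count pre-existing fatigue as Long COVID, and the listed survey items leave no means of separating it afterwards.

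The size cannot be derived from the protocol. With assumed background rates of 5% or 10%, a true 10% appears as 14.5% or 19%, several times the sampling half-width away. With assumed case response of 40% to 70%, selection alone gives 8% to 14%. The illustration covers fatigue from every other cause, not only that from before COVID-19. It therefore shows the order of magnitude at risk, and does not forecast how many respondents have prior CFS/ME.

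**What to change.** Before the survey opens:

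1. Add two survey items: whether the present fatigue began before COVID-19, and whether CFS/ME had been diagnosed before COVID-19. Report prevalence with and without the respondents so identified, removing them from both numerator and denominator in the second figure. Someone with earlier fatigue may have worsened after infection, so present both figures and do not treat the second as the corrected one.
2. In Section 7.5, call the result *prevalence of fatigue caseness (CFQ ≥ 4) at least 12 weeks after a positive test among responding eligible adults*, and bring the wording of Sections 1, 4 and 6 into line. This matches the first aim in Section 5. It is needed even with the new items, because they do not identify unrelated fatigue that began after COVID-19.
3. At the Phase 2 telephone consent call, which already takes place, record whether the person has used the technique before.

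The cost is two or three extra questions, recall error in the onset item, and a less favourable headline figure. The recruitment plan and sample size do not change.
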